Psoriatic arthritis (PsA) is a chronic inflammatory arthritis that can be associated with devastating outcomes including irreversible joint damage. The management of a patient with PsA is extremely challenging due to the high degree of phenotypic heterogeneity. The ultimate goal of this proposal is to prepare pragmatic trials in PsA trials that will encompass all relevant subgroups of patients. The aims of this study specifically focus on responses to biologic therapy among patients with PsA and determining the optimal set of outcome measures for PsA trials.

Objectives

Overall objectives

This is a multi-center cross-sectional study aiming to obtain the data necessary to design a pragmatic trial in PsA including responses to biologic therapy among patients and determine the optimal set of outcome measures for PsA trials.

Primary outcome variable(s)

Aim 1. Determine responses to biologic therapy with among patients with PsA in real world setting. Hypotheses: a) The magnitude of response to TNFi will be lower in a heterogeneous PsA population (ACR20 40%) than in the homogenous RCT populations reported in the literature (ACR20 ~60%). Additionally, the magnitude of response, as defined by multiple outcome measures including ACR20, will be lower in the subset of patients with active disease who would not be eligible for a typical RCT(3 swollen joints) compared to patients who would be eligible for an RCT (3 swollen joints). Rationale: The majority of patients with PsA are not represented in RCTs. To design high quality pragmatic trials with appropriate sample size estimates, response rates in real-life settings are needed.

Secondary outcome variable(s)

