Aim 2. Define the optimal set of outcome measures for pragmatic trials with PsA. Hypothesis: A parsimonious set of instruments will be identified; these outcome measures will be responsive, non-overlapping, and feasible for pragmatic trials. Rationale: Optimal outcome measures for pragmatic trials will be feasible, valid, and responsive across the diverse spectrum of patients with PsA. We will examine the responsiveness, minimal clinically important improvement (MCII) and discrimination of multiple PsA outcome measures. These results will inform selection of the primary and secondary outcomes for pragmatic trials and will also be relevant for traditional RCTs. Because subgroups of patients may respond differently, we will also examine the performance of the outcome measures within subgroups, including subphenotypes (e.g., axial disease, polyarticular, oligoarticular), demographics (e.g., sex), and common comorbidities (e.g., obesity and depression). These analyses will a) identify outcome measures suitable for pragmatic trials, b) determine if outcome measure selection should differ according to PsA subgroups and c) inform stratification variables for pragmatic trials

Background

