Psoriatic arthritis (PsA) is a chronic inflammatory arthritis associated with psoriasis, one of the most common autoimmune skin diseases affecting 2-3% of the population. Despite many advances in disease pathogenesis and therapeutics, approximately half of PsA patients continue to have active disease despite treatment. Therefore, it is imperative to test new treatment modalities including nonpharmacologic therapies and novel management strategies. While randomized controlled trials (RCTs) can address efficacy, or whether a drug can work, the homogenous population selected for inclusion in RCTs is not generalizable to the broader population of patients with PsA (a highly heterogeneous disease). By contrast, pragmatic trials test the effectiveness of management strategies in "real-world" clinical practice as opposed to the highly controlled settings in RCTs. Many important questions facing patients with PsA (e.g., comparative effectiveness) can be addressed with pragmatic trials. However, before this approach can be launched effectively, there is a fundamental need to identify appropriate outcome measures for PsA pragmatic trials. Currently the primary outcome in PsA RCTs, is the American College of Rheumatology 20% Response Criteria (ACR20), an outcome designed for rheumatoid arthritis, a substantially different inflammatory arthritis. Furthermore, the ACR criteria have intrinsic weaknesses that ultimately limit feasibility for a pragmatic trial, including the need for a blood test at two time points and underperformance in the most common PsA subpopulation (the half of patients with less than three swollen and tender joints at therapy initiation). The ultimate goal of this proposal is to prepare pragmatic trials in PsA trials that will encompass all relevant subgroups of patients. Three objectives are envisioned: 1) Examine response in the heterogeneous population of patients that can be enrolled in pragmatic trials and compare those to the subset of patients who would be eligible for a traditional RCT; 2) Define the optimal set of outcomes for use in a pragmatic trial; and 3) Examine how subgroups (e.g., sex, phenotypes, comorbidities) affect outcome measurement. We will address the aims in a prospective observational cohort study conducted within the multicenter Psoriatic Arthritis Research Collaborative (PARC). The four centers will also be the sites for the proposed pragmatic trial. At completion of the Aims, we will have all of the necessary components to initiate a pragmatic trial for PsA: outcomes will be selected, stratification variables identified, sample size calculated, and data collection methods solidified. Additionally, we will identify expectations for treatment response in clinical practice, calculate minimal clinically important improvement, and examine how subgroups affect measurement of response. The results from the proposed studies will additionally inform outcome measures for traditional RCTs and clinical practice.

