Patients may be recruited before or after a new patient visit or return visit. In the case that the visit encounter is completed before enrollment, only the additional information not collected for clinical purposes will be collected. In other words, most of this information is collected in a routine clinic encounter. The information collected during that encounter will be used to complete as much of the CRF as possible and then the additional elements from the CRF will be completed by the research coordinator or site PI following that visit using information from the visit notes. After informed consent is obtained by a member of the study team listed on HS-ERA, a detailed history about the patient's arthritis will be taken and a complete examination will be performed by the rheumatologist. Patients will complete a set of Patient Reported Outcome (PRO) surveys electronically or on paper. Participants may also choose to have the survey link emailed and complete the PRO's within the 2 weeks following the baseline enrollment visit. Results of laboratory tests and radiography obtained for clinical purposes will be recorded. We will record the therapeutic regimen planned at the end of the clinical encounter. This data will be collected by the rheumatologist and the research coordinator at each site. Patients will also undergo a blood draw by venipuncture at the outpatient lab. Approximately 40 mL (4 tubes) of blood will be drawn at each visit. No more than 50 mL will be drawn at each visit. Clinical labs may also be drawn at this time. The study team will pick up the blood, process it, and store it onsite at UPenn/UPHS. The research blood draw will be ordered in EPIC and charged to the study but all other items in this study are considered clinical care and will be charged to insurers/subjects as usual. At a follow up visit approximately 3 months from the initial study visit, a thinned version of the CRF will be used to update the information collected from the participant and record any changes and response to therapy. . The participant will also fill out a different version of patient outcome measurements, have a complete examination performed by a rheumatologist, and undergo a blood draw again. A link to the PRO surveys will be emailed out 2 weeks prior to the scheduled follow-up visit and will be available until 2 weeks after the visit. Participants can also choose to complete the PROs at the visit on paper or electronically. The blood and information collected throughout this study will be used to build a repository for future research projects. The de-identified information stored in the redcap will available to the study teams at each of the sites involved in this study and to those PIs for future research. Researchers not involved in this study will not be permitted to request or use data or samples from this study. Blood samples will be processed and stored at individual sites. Blood samples may be shipped to a central location for further testing but will not be made available to outside researchers. Further testing will be focused on bio-markers of treatment response and disease progression. Participants may retract permission and ask that their samples be destroyed.

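### Aim 2 would decide from separate within-subgroup results whether outcome measures should differ by subgroup, and would select and estimate from one cohort, with no between-subgroup contrast or internal validation

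*Combined protocol and SAP*

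**What the plan says.** Under Secondary outcome variable(s), Aim 2 sets out the task: "We will examine the responsiveness, minimal clinically important improvement (MCII) and discrimination of multiple PsA outcome measures". It then gives the use: "These results will inform selection of the primary and secondary outcomes for pragmatic trials". The expected product is stated as a hypothesis: "A parsimonious set of instruments will be identified; these outcome measures will be responsive, non-overlapping, and feasible for pragmatic trials".

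The same section plans to look at performance within subgroups. It names six examples: axial, polyarticular and oligoarticular disease, sex, obesity and depression. One stated purpose is to "determine if outcome measure selection should differ according to PsA subgroups".

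The change data have one source. Procedures describes a baseline visit and then reassessment: "At a follow up visit approximately 3 months from the initial study visit". No second sample is described.

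Background says that on completion of the aims "outcomes will be selected, stratification variables identified, sample size calculated, and data collection methods solidified".

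The Analysis Plan covers description by center, a chi-squared test of phenotype prevalence between centers, and ANOVA or Kruskal-Wallis tests of severity and psoriasis duration between centers. It gives no candidate list, responsiveness statistic, selection rule, holdout or resampling step, or comparison between subgroups.

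**The concern.** There are two linked problems, and the first is the larger.

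1. Whether selection should differ between subgroups is a question about a difference between subgroups. Examining performance inside each subgroup and comparing the results by eye does not estimate that difference or its uncertainty. Rankings of instruments with similar responsiveness are unstable at subgroup sizes, so two subgroups can appear to need different measures when nothing distinguishes them.

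2. An instrument chosen partly because it looked responsive in this cohort will tend to look more responsive here than it is. The excess is small in the full cohort and larger in subgroups.

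At stake is the study's main deliverable, the outcome set for a pragmatic trial, together with any advice to use different measures in different kinds of patient.

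**Working it through.** **The plan's own figure.** The only power statement is 82% for a one-way ANOVA across centers with 20 per group, a range of means of 5.5 and SD 5. With two centers at the extremes and two at the grand mean, the noncentrality is 20 × (2.75² + 2.75²)/25 = 12.1 on 3 and 76 degrees of freedom. Power is then 82.3%, so the figure reproduces. It concerns center differences and says nothing about Aim 2.

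**Inputs from the documents.** Characteristics of the Study Population lists 55 subjects at the lead site and 220 under collaborating researchers. The total is 220 if that figure covers all four centers (4 × 55), or 275 if the two are added. I use 220, with 110 and 55 as illustrative subgroup sizes (a half and a quarter).

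**Assumptions, none stated in the documents.**
- 5 to 10 candidate instruments
- Correlation of change scores between instruments 0.3 to 0.6
- SRM (mean change divided by SD of change) as the responsiveness statistic
- The top-ranked instrument is chosen
- True SRMs either spread evenly over 0.3 to 0.8, or all equal to 0.6

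**Why rankings are unstable.** The standard error of an SRM δ is roughly √((1 + δ²/2)/n). At δ = 0.6 it is √(1.18/n): 0.07 at n = 220, 0.10 at 110 and 0.15 at 55. If SRMs spread evenly over 0.3 to 0.8, neighboring instruments lie 0.5/4 = 0.125 apart with 5 candidates and 0.5/9 = 0.056 apart with 10. The sampling error is of the same order as the gaps.

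**Simulation.** Draw equicorrelated normal change scores, compute each SRM, take the largest, and subtract that instrument's true SRM. For discordance, draw two independent subgroups with the same true SRMs and record whether the top instrument differs.

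| Quantity | n | True SRMs spread 0.3 to 0.8 | All equal to 0.6 |
|---|---|---|---|
| Overstatement of top SRM | 220 | 0.01 to 0.05 | 0.06 to 0.10 |
| Overstatement of top SRM | 55 | 0.06 to 0.15 | 0.13 to 0.21 |
| Different top instrument | 110 each | 20 to 57% | 80 to 90% |
| Different top instrument | 55 each | 35 to 69% | 80 to 90% |

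The low ends come from 5 candidates and the high ends from 10. Repeat runs agreed to about two percentage points on discordance. The 80 to 90% in the last column carries no information about this study. With K equal candidates, two independent picks differ with probability 1 − 1/K, which is 0.80 for K = 5 and 0.90 for K = 10 at any subgroup size.

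**Does correction work?** With 10 candidates and correlation 0.5, bootstrapping the selection step reduces the excess from 0.04–0.09 to 0.00–0.02 at n = 220, and from 0.12–0.19 to 0.01–0.05 at n = 55.

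**The case against.** The strongest reply is that the documents do not state a bad method; they state none. Aim 2 says that performance within subgroups will be examined and that results will inform selection. It does not say that the highest-ranked instrument wins, or that each subgroup will get its own choice. Feasibility, non-overlap, validity and discrimination also count, and a set is sought rather than one winner. All of that stands. It makes the overstatement figures upper ones for their assumptions, and it limits the point to an omission. It does not supply the missing comparison, because the question about subgroups is put explicitly and nothing in the plan can answer it.

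A second reply is that the sizes depend on the number and spread of candidates, which are unknown. This also stands, so the figures are illustrations. Under the spread assumption the full-cohort bias is minor.

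A reader might also infer that the later trial will be too small because inflated SRMs feed its sample size. The documents do not support that. Their one explicit link to sample size is the Aim 1 rationale: "To design high quality pragmatic trials with appropriate sample size estimates, response rates in real-life settings are needed". Everyone in the cohort starts a TNF inhibitor, so an SRM here is a within-patient change and not a difference between arms. Background promises a sample size without saying that Aim 2 responsiveness will be its input.

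**Conclusion.** The point holds as an omission that is cheap to repair. As written, the plan cannot distinguish a real subgroup difference in instrument performance from a chance one, and it would report responsiveness from the same data that informed selection.

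The subgroup part matters most. Under the spread assumption, identical subgroups of 110 may disagree on the top instrument in about 20 to 57% of samples. The overstatement of responsiveness is modest in the full cohort (0.01 to 0.05, or up to 0.10 if all candidates are equal) and more noticeable at n = 55 (0.06 to 0.15, or up to 0.21). All of this rests on assumed candidate numbers, correlations, true SRMs and subgroup sizes, and on a top-rank rule that the documents do not state.

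Two further inferences are not supported. One is that subgroup choices will differ by chance: they may, at a rate that depends on how far the candidates truly differ. The other is that the MCII needs the same optimism correction: the documents give no MCII method, and nothing calculated here shows that selecting on responsiveness biases it.

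**What to change.** Add an Aim 2 section to the Analysis Plan that does the following.

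- List the candidate instruments, the responsiveness statistic and the selection rule, including how feasibility and non-overlap enter.
- For each candidate, estimate the difference in responsiveness between subgroups with a bootstrap confidence interval (an instrument-by-subgroup contrast). Recommend a different instrument for a subgroup only when that difference is supported. Define support in advance, because six example subgroups and several instruments give many contrasts.
- Bootstrap the whole selection step, or select in three centers and estimate in the fourth, rotating. Report optimism-corrected responsiveness with 95% confidence intervals for the selected instruments.
- If any Aim 2 estimate is used to plan the later trial, use the corrected value.

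The cost is analysis programming and some added text, with no new data. Reported responsiveness will be slightly less favorable, and there will be fewer subgroup-specific recommendations. The contrasts will be imprecise: from the standard errors above, the 95% half-width for a difference between two subgroups is about 1.96 × √2 × 0.104 = 0.29 at 110 each and 1.96 × √2 × 0.146 = 0.41 at 55 each. The report should show that uncertainty.

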The study team is composed of 5 investigators with diverse and complementary talents and experiences that are in line with the study goals. All investigators are members of the Group for Research and Assessment of Psoriasis and Psoriatic Arthritis (GRAPPA) and all collaborate extensively with local psoriasis experts. Furthermore, all four centers have already been collecting data from patients in their PsA clinics, have published on many topics in PsA, and hold grants from a variety of sources. All four centers have outstanding scientific environments with supportive of division directors and track records for successful competition for NIH funding. The scientific environments at all four institutions are outstanding. All institutions have unmatched resources for clinical and translational research and all investigators have access to institutional Clinical and Translational Science Award (CTSA) resources. Additionally, all of the investigators have published studies in psoriatic arthritis and are active members within GRAPPA. Given that each center sees approximately 40-60 new patients with PsA each year, obtaining 55 new or return patients within the study period is feasible. Aligning data capture among our centers through completion of this study will allow for continued uniform data capture and collaboration. Furthermore, this model is sustainable and low cost as primary data is collected and stored within each institution primarily and data will be transferred into the PARC database as needed. Thus, the model could be modified by each institution to serve other ongoing studies and could be extended to other sites in the future.

Characteristics of the Study Population

Target population

Rheumatology clinic patients with active PsA switching to or adding a TNFi.

Subjects enrolled by Penn Researchers

55

Subjects enrolled by Collaborating Researchers

220

Accrual

Patients seen by any rheumatology provider will be recruited at their new patient visit or return visit. Flyers about the study will be posted in examination rooms and rheumatology practitioners within the division will be educated about the study. The Penn Psoriatic Arthritis Clinic sees approximately 65-75 patients with psoriatic arthritis per year.

Key inclusion criteria

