-Age 18-89 -Active PsA (at least one swollen joint or enthesitis) -Meet CASPAR criteria (Table 2) (103) -Initiation of TNFi (etanercept, adalimumab, infliximab, certolizumab, golimumab) (At the time of the submission of this grant, TNFi biosimilars have been approved by the FDA but are not available on the US market. Once available, patients starting TNFi biosimilars will similarly be eligible for participation. Patients may have been on the medication in the past but must have had greater than 2 months off the medication. Patients may be taking other traditional DMARDs. A washout period is not required.)

Key exclusion criteria

-Unable to give informed consent -Out of the age range -Switching therapies for skin psoriasis in the setting of well controlled joint and enthesis symptoms. -Patients with only active PsA

Vulnerable Populations

Children Form

Pregnant women (if the study procedures may affect the condition of the pregnant woman or fetus) Form

Fetuses and/or Neonates Form

Prisoners Form

Other

x None of the above populations are included in the research study

The following documents are currently attached to this item:

There are no documents attached for this item.

Populations vulnerable to undue influence or coercion

Although not directly targeted, mentally disabled persons, economically or educationally disadvantaged persons, and/or employees or students of the University of Pennsylvania will not be denied enrollment and any special protections and/or additional safeguards will be undertaken in order to protect the rights and welfare of these subjects from coercion or undue influence as appropriate.

Subject recruitment

Patients seen by any rheumatology provider may be recruited by the study team (as listed in HS-ERA) at their new patient visit or return visit. Flyers about the study will be posted in examination rooms and rheumatology practitioners within the division will be educated about the study.

Will the recruitment plan propose to use any Penn media services (communications, marketing, etc.) for outreach via social media avenues (examples include: Facebook, Twitter, blogging, texting, etc.) or does the study team plan to directly use social media to recruit for the research?

No

The following documents are currently attached to this item:

There are no documents attached for this item.

Subject compensation*

Will subjects be financially compensated for their participation? Yes

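### The exclusion list bars patients with only active PsA, which conflicts with the inclusion criterion and the target population; the line is unexplained and the lists need reconciling

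*Combined protocol and SAP*

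**What the plan says.** All the text is in the combined protocol and SAP.

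- **Key inclusion criteria** requires "Active PsA (at least one swollen joint or enthesitis" (the parenthesis closes there), together with CASPAR criteria, the age range and initiation of a TNF inhibitor.
- **Key exclusion criteria** lists inability to consent, age out of range, a change of therapy made for skin disease while joints and entheses are well controlled, and finally "Patients with only active PsA".
- **Target population** reads "Rheumatology clinic patients with active PsA switching to or adding a TNFi".
- **Primary outcome variable(s), Aim 1** hypothesises that "The magnitude of response to TNFi will be lower in a heterogeneous PsA population (ACR20 40" percent, against about 60 percent in published trials. Its rationale is that "To design high quality pragmatic trials with appropriate sample size estimates, response rates in real-life settings are needed".
- **Background** gives the first objective as "Examine response in the heterogeneous population of patients that can be enrolled in pragmatic trials" and comparing them with the subset eligible for a traditional trial.

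The documents do not define *only* in the last exclusion, give a reason for it, or require a second active condition.

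**The concern.** Eligibility criteria decide who contributes to the Aim 1 response rate. Here one list requires a condition and the other excludes patients for having it, or for having nothing else. A coordinator who follows the exclusion as written turns away some or all of the patients the study is meant to describe. A coordinator who follows the inclusion criterion ignores a listed exclusion.

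Two things are at stake. First, the ACR20 rate is meant to describe a broad, real-world population and to inform the sample size of a later pragmatic trial. An unstated restriction would change the population to which that rate applies. Second, four centres enrol, and the Analysis Plan compares phenotype prevalence and disease severity between them. If centres interpret the line differently, a screening difference could look like a difference between clinics. That is a risk created by the wording, not something the documents show to have happened.

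**Working it through.** No arithmetic underlies the point, so the check sets the texts side by side.

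1. **The line without weight on *only*.** Inclusion requires active PsA and exclusion removes active PsA. No patient can satisfy both lists, and the whole target population is barred.

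2. **The line with *only* meaning no other active condition.** The overlap is partial. A patient with a swollen joint, CASPAR-positive disease, a new TNF inhibitor and no other active condition meets every inclusion criterion and the target population, yet is excluded. Neither the target population nor the inclusion list asks for a second active condition, and Aim 1 and Background speak of a heterogeneous population.

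3. **The line with a wrong or missing word.** The intended rule cannot be reconstructed from the documents.

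4. **Comparison with the neighbouring exclusion.** The item just before it removes patients whose treatment change is for skin while joints and entheses are quiet. That agrees with an inclusion criterion built on joint or entheseal activity. The disputed line does not.

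5. **Could it be a text-reading artefact?** Symbols do seem to have been lost elsewhere: the Analysis Plan shows a significance level with no symbol before the equals sign, and Aim 1 gives its two opposed groups the same swollen-joint label. The disputed line is a complete phrase with no visible gap, so a lost symbol is not an evident explanation. A lost word cannot be ruled out, which is why the source file has to be checked.

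6. **Size.** Let s be the share of otherwise eligible patients removed, and d the ACR20 rate in those kept minus the rate in those removed. The shift in the estimate is

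   rate in kept − [(1 − s) × rate in kept + s × rate in removed] = s × d.

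   The documents give neither s nor d, nor the sign of d. If s = 0 the shift is 0. If s = 1, as in step 1, nobody is enrolled and there is no estimate. Nothing in the documents narrows the range between these.

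**The case against.** The strongest reply is that narrowing an included group is what exclusions do. Read with *only* in force, the line picks out a subset of patients with active PsA, so it is not a flat contradiction. That stands: the conflict is total only if *only* is disregarded. It does not rescue the line, because the restriction is undefined, unexplained and at odds with the target population.

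A second reply is that the target population and inclusion criterion make the intention clear enough for sites to enrol correctly. They may well do so, and then the effect is zero. But this is an operative criterion, and sites should not have to decide which list to follow.

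A reader might also infer more than the documents support:

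- **That a phenotype word such as axial was dropped, so the line is harmless.** Secondary outcome variable(s), Aim 2, does name "subphenotypes (e.g., axial disease, polyarticular, oligoarticular", but nothing links that list to the exclusion. The inclusion criterion is also met by enthesitis alone, and the documents do not say that axial disease rules out enthesitis, so an axial-only exclusion is not shown to leave enrolment unchanged. A slip related to skin disease is no less plausible, given the adjacent item.
- **That the bias is small, or large.** Any bound depends on the values chosen. With s = 50 percent, d = 10 points gives 0.5 × 10 = 5 points and d = 15 points gives 0.5 × 15 = 7.5 points. Both values of d, and s itself, are arbitrary.
- **That patients were wrongly excluded, or that the cohort is invalid.** The documents record no exclusion under this line.

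**Conclusion.** The point holds as an internal conflict in the eligibility text. The last key exclusion cannot be reconciled with the inclusion criterion and target population as written: the conflict is complete on one reading and partial on the other. That it is probably a wording slip is an inference, which the documents neither confirm nor refute.

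The consequence for the ACR20 estimate is not computable, has no supported direction, and may be zero if sites enrol by the inclusion criterion. The conclusion assumes only that the line reads in the source file as it does here. The line should be corrected because it is an operative rule and the correction is cheap. It is not evidence that the study's results are wrong.

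**What to change.** 1. Check the line against the source file. The inclusion text contains the phrase "At the time of the submission of this grant", which suggests that the eligibility wording was carried over from a grant application, so that application is a natural place to look.
2. Reconcile the two lists before they are applied at the four sites. If no further restriction was intended, delete the line. If one was intended, the investigators should state the qualifier so that it agrees with the inclusion criterion and the target population, and describe the Aim 1 population accordingly. The choice is theirs; the documents do not settle it.
3. The documents do not mention screening records. If they are kept, look for patients excluded under this line and report how many there were, by centre.

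The cost is one look at a source file, a one-line amendment sent to all sites and, where records exist, a short review of them. Sample size and analysis methods need not change unless a real restriction turns out to have been intended.
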